8.6.1 Follow-up until progression

Whenever possible, a patient who has discontinued study treatment for other reason than progressive disease will be followed up at 3-monthly intervals until progression including the following assessments:

- **Clinical assessments** (including ECOG performance status, blood pressure, pulse)
- **Tumor imaging (CT or MRI):** evaluation of time-point response by comparison with target and non-target lesions at time of Best Response
- **Quality of Life:** questionnaires

Anticipated exceptions from follow-up will be “withdrawal of consent”, “lost to follow-up”, “patient moved”.

Follow-ups until progression will be suspended in patients in whom a new cancer treatment has been started without prior documentation of progressive disease. The start date of the new systemic therapy (or local therapy directed to lesions on which response assessment was based) will be documented.

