2 OBJECTIVES

Primary:

1. Compare the overall survival of patients treated with AEZS-108 to the OS of patients treated with doxorubicin

Secondary:

1. Compare efficacy based on progression-free survival (PFS), overall response rate (ORR), and clinical benefit rate (CBR).
Subgroup analyses of efficacy parameters in relation to tumor LHRH receptor expression.
2. Compare safety.
3. Determine the impact of these regimens on patient-reported quality of life during and for up to 1 year after completion of study treatment.
4. Assess the pharmacokinetics and exposure-response relationships of AEZS-108, doxorubicin and doxorubicinol in a PK sub-study at selected sites and by sparse PK sampling, respectively.
5. Assess the acute effects on electrocardiographic parameters (e.g., QT/QTc interval) within PK sub-study.

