8.6.2 Follow-up for survival

For patients going off study, survival information will be collected at 3-month intervals, telephone contact is acceptable.

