#### 7.2.7.2 Mixed Model Analysis

##### 7.2.7.2.1 Hypothesis

The hypothesis for the HRQL endpoint – change over time in the QLQ-C30 GHS/QOL is as follows:

- H0: There is no difference in health-related quality of life based on the EORTC QLQ C-30 GHS/QOL scale between AEZS-108 and doxorubicin treated subjects.
- Ha: Treatment with AEZS-108 is associated with better health-related quality of life based on the EORTC QLQ C-30 GHS/QOL scale as compared to treatment with doxorubicin.

The same set of hypotheses holds for QLQ-EN24.

HRQL assessments are performed at the following visits:

Screening, end of cycles 3 and 6, end of therapy (3-5 weeks after last dose) and at post therapy follow-up (every 3 months).

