#### 7.2.7.2.3 Description of mixed model with assumptions

Changes over time in QLQ-C30 Global Health Status/QOL scores and in QLQ-EN24 scores will be compared between treatment groups using a restricted maximum likelihood-based mixed model for repeated measures (MMRM) data under the missing at random (MAR) assumption (Mallinckrodt et al, 2008).

The dependent variable of this model will be the change of QLQ-C30 Global Health Status/QOL score or the QLQ-EN24 score measured at the end of cycles 3 and 6, at the end of therapy and at post therapy follow-up as compared to baseline (denoted by HRQL). The model will include the fixed, categorical effects of treatment (trt), visit (visit), and treatment-by-visit interaction (trt\*visit). As there is only a limited amount of time points per subject and given the possibility that not all time points are equally spaced in time, time is entered into the model as the categorical variable visit. The random subject effects

are not explicitly formulated in the model form, but will be modelled as part of the within-subject error correlation structure. For this purpose, an unstructured covariance matrix will be used, allowing for different variances / covariances across subjects. If the analysis using the unstructured covariance matrix fails to converge, the following covariance structures will be tested: heterogeneous Toeplitz, heterogeneous compound symmetry, Toeplitz and compound symmetry. The covariance structure converging to the best fit, as determined by Akaike's information criterion, will be used as the primary analysis. The Kenward-Roger approximation will be used to estimate denominator degrees of freedom. The least square means for each treatment group and the treatment difference will be presented together with the 95% confidence interval and p-value.

The pseudo SAS code of the primary model is as follows:

```
proc mixed data = HRQLdataset method = reml;
  class PatID trt visit;
  model HRQL = trt visit trt*visit baseline baseline*visit / noint ddfm = kr;
  repeated r / subject = PatID type=un;
run;
```

where PatID represents the individual subject id.

The mixed model will provide estimates of the treatment effect and of the treatment difference at each visit until end of treatment, together with their 95% confidence intervals.

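### The quality-of-life objective runs to 1 year after treatment, but post-treatment questionnaires are due only before progression or new therapy, and no between-arm contrast is clearly planned there

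*Protocol*

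**What the plan says.** **Objective.** Secondary objective 3 in Protocol Section 2 reads "Determine the impact of these regimens on patient-reported quality of life during and for up to 1 year after completion of study treatment". SAP 2.1 repeats it. The protocol synopsis gives the QoL objective without a time horizon.

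**Collection.** Protocol 8.5 requires the questionnaires at the end-of-therapy visit, 3 to 5 weeks after the last dose, for every patient going off treatment. Beyond that visit they appear only in Protocol 8.6.1, which covers a patient who has "discontinued study treatment for other reason than progressive disease will be followed up at 3-monthly intervals until progression". The same section adds: "Follow-ups until progression will be suspended in patients in whom a new cancer treatment has been started without prior documentation of progressive disease". Protocol 8.6.2 lists nothing but vital status: "survival information will be collected at 3-month intervals, telephone contact is acceptable".

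**Flow chart.** In the post-therapy column (Protocol flow chart and SAP Appendix A), ECOG status and blood pressure/pulse are limited to the period before progression. The QoL row has an unqualified X.

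**Analysis.** SAP 7.2.7.2.1 lists 3-monthly post-therapy follow-up among the QoL visits. SAP 7.2.7.2.3 includes those visits in the dependent variable of the MMRM, with visit as a categorical effect and a treatment-by-visit interaction. Its closing sentence says the model will give "estimates of the treatment effect and of the treatment difference at each visit until end of treatment". SAP Appendix E plans raw and change-from-baseline QoL tables with no cut at end of treatment.

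**The concern.** The objective, the collection rule and the reporting rule cover three different periods. A patient who stops because of progression has no questionnaire due after the end-of-therapy visit. One who progresses or starts another therapy later has none due from then on. The patients who remain are selected by events after randomisation, and there are more of them in whichever arm has the longer PFS. A difference between arms in that group is not a randomised comparison of the regimens.

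The MMRM does not repair this. Under its missing-at-random assumption, scores after progression are inferred from scores before it, yet progression is a point at which QoL may well change. SAP 7.2.7.2.2 itself concedes that missingness not at random may not be completely ruled out.

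At stake is what the report may conclude about the year after treatment. QoL is not a key secondary endpoint and lies outside the OS-PFS-ORR hierarchy in SAP 7.4, so no confirmatory conclusion is affected.

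**Working it through.** **1. The texts side by side**

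| Source | Period covered | Patients covered |
|---|---|---|
| Protocol 2, SAP 2.1 | Treatment and up to 1 year after | All, by implication |
| Protocol 8.5 | End-of-therapy visit | All going off treatment, including for progression |
| Protocol 8.6.1 | 3-monthly, until progression or new therapy | Those who stopped for another reason |
| Protocol 8.6.2 | 3-monthly, survival status only | All going off study |
| SAP 7.2.7.2.3, dependent variable | Includes post-therapy visits | As collected |
| SAP 7.2.7.2.3, closing sentence | Differences until end of treatment | As collected |

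No section names a 1-year time point, a post-treatment contrast, or how progression and death are handled for QoL.

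**2. Illustration of the gap**

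The plan states no QoL completion rate or sample size, so there is no figure of its own to reproduce.

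Inputs from the documents:
- At most nine 3-week cycles of AEZS-108 (Protocol 6.1.2). At 60 mg/m² with a ceiling of 550 mg/m² (Protocol 6.2.3), doxorubicin also allows nine full-dose cycles (550/60 = 9.2).
- OS medians of 9 and 12 months (Protocol 9.10).
- Median TTP of about 7 months in the Phase II study of AEZS-108 (Protocol 1.2.2). This is not PFS, and Protocol 1.3 notes that only 8 patients in that study were platinum/taxane pretreated.

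Assumptions: exponential curves, all nine cycles given without delay, and PFS medians of 4 and 5 months (the documents assume none), with 7 months as the favourable case.

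Treatment time: 9 × 21 / 30.4375 = 6.2 months. Six and 12 months after treatment are then t = 12.2 and t = 18.2 months from randomisation.

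Formulas: S(t) = 0.5^(t/median). Share of survivors with no questionnaire due = 1 − S_PFS(t) / S_OS(t), from unrounded values.

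| PFS / OS median (months) | t (months) | Progression-free | Alive | No questionnaire due |
|---|---|---|---|---|
| 4 / 9 | 12.2 | 12.1% | 39.1% | 69% |
| 5 / 12 | 12.2 | 18.4% | 49.4% | 63% |
| 7 / 12 | 12.2 | 29.8% | 49.4% | 40% |
| 4 / 9 | 18.2 | 4.3% | 24.6% | 83% |
| 5 / 12 | 18.2 | 8.0% | 34.9% | 77% |
| 7 / 12 | 18.2 | 16.5% | 34.9% | 53% |

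The 7-month figure was observed on AEZS-108, so it is paired with that arm's OS median. Against the control median it would give 1 − 0.165/0.246 = 33% at 18.2 months. A 3-month PFS median with 9-month OS would give 1 − 0.015/0.246 = 94%.

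**3. Limits of the illustration**

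Patients on new therapy before progression are not deducted, which understates the gap. Few patients would complete nine cycles: with a 4-month PFS median only 34% are progression-free at 6.2 months. For those who stop earlier, the post-treatment year starts earlier than the table assumes. If they stopped for progression, no post-therapy questionnaire is due at all.

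**The case against.** **A reader might infer that the post-treatment question cannot be answered at all.** The documents do not support that. The end-of-therapy questionnaire covers patients who stopped for progression. Three-monthly data follow in those who stopped for other reasons. The post-therapy visits are in the MMRM, whose treatment-by-visit term could give a contrast at each of them. SAP 7.2.7 and an earlier sentence of SAP 7.2.7.2.3 promise treatment differences without a visit limit, so only the closing sentence excludes them. The descriptive tables are not truncated. This stands: the defect is a mismatch and a restricted group, not an absence of data.

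**A reader might infer from the unqualified X that sites will continue questionnaires after progression.** That is weak evidence. The tumour-imaging row has the same X, although imaging under 8.6.1 ends at progression. Footnote 6 ties the 3-monthly reassessment to patients who stopped for other reasons. The row should be made consistent, but it does not override 8.6.1.

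**The horizon is a ceiling.** The wording does not promise an estimate at exactly 1 year or in every survivor. That is fair, but some planned comparison after treatment is still needed to support the objective, and none is clearly specified.

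**Stopping at progression is defensible.** Later treatment is at the investigator's discretion (Protocol 6.4), so later scores would mix in its effects. Continuing would add 54 self-completed items, some on sexual function, to what may be a telephone survival contact at about 120 sites. This also stands, and it is why more data collection is not asked for here.

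**The bias may not reach a reported result.** If differences are reported only until end of treatment, the selected post-therapy comparison is not a headline model estimate. That is correct, but the stated objective then goes unaddressed by the model.

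**Conclusion.** The concern holds in this form: the objective extends up to 1 year beyond treatment, while the plan supports only a description of post-treatment QoL in patients who are alive, progression-free and without new therapy. No between-arm contrast is clearly planned for that period, and SAP 7.2.7.2.3 disagrees with itself on which visits matter.

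The text comparison needs no assumption. The size does. Roughly half to four-fifths of survivors would have no questionnaire due at 1 year after treatment, given exponential curves, nine cycles and the PFS medians shown. The exact share moves with the PFS median, which the documents do not supply, so it should be read as an order of magnitude.

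This should be corrected because it changes what the trial may claim about QoL. It does not touch the primary or key secondary analyses.

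**What to change.** 1. In Protocol 2 and SAP 2.1, restate objective 3 as QoL during treatment through the end-of-therapy visit. The synopsis already omits the 1-year horizon.
2. In SAP 7.2.7.2.3, remove post-therapy visits from the MMRM, so that modelled and reported visits agree.
3. Tabulate post-therapy QoL descriptively by arm under the label *patients alive, progression-free and without new therapy*, showing at each time point the number alive and the number completing the questionnaire.
4. Mark the QoL row of the flow chart, in the protocol and in SAP Appendix A, consistently with Protocol 8.6.1.

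The cost is wording and two columns of counts. The downside is a narrower claim.

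If the sponsor wants to keep the 1-year objective, the alternative is to collect questionnaires at the existing 3-monthly contacts regardless of progression or new therapy, and to specify the arm difference at those times. That needs an amendment and adds burden for patients and sites. It is an option, not a required correction.

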7.1.5 Response Criteria

7.1.5.1 Evaluation of Target Lesions

Complete Response (CR): Disappearance of all target lesions. Any pathological lymph nodes (whether target or non-target) must have reduction in short axis to <10 mm.

Partial Response (PR): At least a 30 % decrease in the sum of the diameters of target lesions, taking as reference the baseline sum diameters.

Progressive Disease (PD): At least a 20 % increase in the sum of the diameters of target lesions, taking as reference the smallest sum on study (this includes the baseline sum if that is the smallest on study). In addition to the relative increase of 20 %, the sum must also demonstrate an absolute increase of at least 5 mm. (Note: the appearance of one or more new lesions is also considered progressions).

Stable Disease (SD): Neither sufficient shrinkage to qualify for PR nor sufficient increase to qualify for PD, taking as reference the smallest sum diameters while on study.

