7.1.5.2 Evaluation of Non-Target Lesions

Complete Response (CR): Disappearance of all non-target lesions and normalization of tumor marker level. All lymph nodes must be non-pathological in size (<10 mm short axis).

Note: If tumor markers are initially above the upper normal limit, they must normalize for a patient to be considered in complete clinical response.

Non-CR/Non-PD: Persistence of one or more non-target lesion(s) and/or maintenance of tumor marker level above the normal limits.

Progressive Disease (PD): Appearance of one or more new lesions and/or unequivocal progression of existing non-target lesions. Unequivocal progression should not normally trump target lesion status. It must be representative of overall disease status change, not a single lesion increase.

Although a clear progression of “non-target” lesions only is exceptional, the opinion of the treating physician should prevail in such circumstances, and the progression status should be confirmed at a later time by the review panel (or Principal Investigator).

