7.1.6 Duration of Response

Duration of overall response: The duration of overall response is measured from the time measurement criteria are met for CR or PR (whichever is first recorded) until the first date that recurrent or progressive disease is objectively documented (taking as reference for progressive disease the smallest measurements recorded since the treatment started).

The duration of overall CR is measured from the time measurement criteria are first met for CR until the first date that progressive disease is objectively documented.

Duration of stable disease: Stable disease is measured from the start of the treatment until the criteria for progression are met, taking as reference the smallest measurements recorded since the treatment started, including the baseline measurements.

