8.5 Procedures at end of study treatment

A patient who is going off study treatment (see [Section 5.3](#)) – will have the assessments/investigations specified below.

As an end-of-cycle assessment, it should be scheduled 3 to 5 weeks (Day 21 to 35) after the last dose. Additional visits/assessments may be indicated to follow-up unresolved adverse events.

- **Interval history** and symptom-directed examination
- **Clinical laboratory** tests (hematology, chemistries, urinalysis, hormones)
- **Cardiac function:**
 - 12-lead electrocardiogram (ECG)
 - Left ventricular ejection fraction (LVEF): Echocardiogram or MUGA
- **Quality of Life:** questionnaires
- **Tumor imaging (CT or MRI):** evaluation of time-point response by comparison with target and non-target lesions defined at screening (baseline)
- **Final evaluations:** best response, reason for discontinuation, investigator's overall judgment on tolerability of study treatment

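### Section 8.6.1 judges off-treatment scans against the lesions at Best Response, while Section 7.1 defines progression against the smallest sum on study; for target lesions this can delay PD

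*Protocol*

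**What the plan says.** **The definition of progression.** Protocol Section 7.1.5.1 defines target-lesion PD as "At least a 20 % increase in the sum of the diameters of target lesions, taking as reference the smallest sum on study", and adds that "this includes the baseline sum if that is the smallest on study". It also requires that "the sum must also demonstrate an absolute increase of at least 5 mm". Sections 7.1.5.3 and 7.1.6 repeat the reference: "taking as reference for progressive disease the smallest measurements recorded since the treatment started".

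**The off-treatment instruction.** Section 8.6.1 covers patients who stopped study treatment for a reason other than progression. They are imaged at 3-month intervals, with "evaluation of time-point response by comparison with target and non-target lesions at time of Best Response".

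**The other visit instructions.** Sections 8.4.5 (end of Cycles 3 and 6) and 8.5 (end of treatment) refer to the target and non-target lesions identified at screening.

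**Non-target and new lesions.** Section 7.1.5.2 sets a qualitative rule: "Appearance of one or more new lesions and/or unequivocal progression of existing non-target lesions". It uses no sum and no nadir.

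**The SAP.** Appendix B takes the RECIST criteria from Protocol Section 7.1 and then gives rules for dating progression. SAP Section 7.2.3 runs duration of response and of stable disease to the first observed PD. SAP Section 7.2.4 gives the PFS censoring table.

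**The concern.** The instruction a site follows at an off-treatment visit names a different reference from the definition of PD. Best Response is a response category (7.1.5.3), and several scans can share it. A patient who first meets PR at the end of Cycle 3 and shrinks further by Cycle 6 is in PR at both. Neither document says which of these scans is the time of Best Response. Section 7.1.6 starts duration of response when CR or PR is first met, so a site could reasonably take that first scan, although the nadir came later.

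The dates of PD feed duration of response, duration of stable disease and possibly PFS. PFS is the first key secondary endpoint, tested after OS for a potential labeling claim (SAP 7.4). The trial is open-label and no central tumor read is described. Secondary efficacy data are source-verified at the 20% level (Protocol 10.6.1). SAP Appendix B does not say that PD will be re-derived from the recorded sums.

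**Working it through.** The plan states no figure on this point, so there is none to reproduce. The check applies the protocol's own PD rule to both references.

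**Rule (7.1.5.1).** For a reference sum R in mm, target-lesion PD is called when the current sum reaches max(1.2 × R, R + 5).

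**Direction for target lesions.** The nadir is the minimum over baseline and all later scans, so the sum at any Best Response scan is at least the nadir. The threshold rises with R. Any sum that is PD against Best Response is therefore also PD against the nadir, and the reverse does not hold.

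**Main example (illustrative sums).** Baseline 100 mm; Cycle 3, 68 mm (first PR, taken as Best Response); Cycle 6, 50 mm (still PR, nadir); then off treatment.
- Threshold against the nadir: 1.2 × 50 = 60 mm.
- Threshold against Best Response: 1.2 × 68 = 81.6 mm.
- A follow-up sum of 62 mm is 62/50 = 1.24 of the nadir (+24%, +12 mm), which is PD. It is 62/68 = 0.91 of the Best Response sum (−9%), which is not PD.

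**Other illustrative courses (baseline 100 mm throughout).**

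| Course | Nadir | Best Response sum | PD threshold, nadir | PD threshold, Best Response |
|---|---|---|---|---|
| PR at 65, then 50 | 50 | 65 | 60 | 78 |
| SD at 95, then 75 | 75 | 95 | 90 | 114 |
| SD at 110 only | 100 (baseline) | 110 | 120 | 132 |
| PR at 50, then 58 | 50 | 50 | 60 | 60 |

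The last row shows no difference, because Best Response and nadir are the same scan.

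**Simulation of direction.** Target-lesion sums were simulated with assumed random growth, taking Best Response as the first scan in the best category. In 54,430 + 52,811 = 107,241 courses without PD on treatment, the Best Response reference called PD earlier in 0, later in 54,430, and with no difference in 52,811. The split depends on the growth assumptions; the zero does not.

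**Length of delay (assumption: the sum doubles in 3 to 6 months).** Going from one threshold to the other takes log2(68/50) = 0.444 doublings, or 1.3 to 2.7 months. With 70 mm at Best Response and a nadir of 40 mm it takes log2(70/40) = 0.807 doublings, or 2.4 to 4.8 months. With scans every 3 months, and crossing times assumed uniform between scans, a shift of 1.3 to 2.7 months skips a scan in about 1.33/3 = 44% to 2.66/3 = 89% of cases.

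**Non-target lesions.** Suppose there are two at baseline, one is absent at Best Response, and it is visible again off treatment. Against the Best Response state this can be read as new or worsening, hence PD. Against the screening lesions it is persistence, hence Non-CR/Non-PD. Here the 8.6.1 reference can bring the call forward. Patients with only non-measurable disease are eligible (5.1) and have no sum at all.

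**The case against.** **Section 7.1 remains the definition.** The nadir rule appears three times, and SAP Appendix B points to it. Section 8.6.1 is a visit-procedure bullet. A reader might infer that the nadir rule has been replaced off treatment; the documents do not support that. This stands: it is an unreconciled contradiction. It still matters, because 8.6.1 is what the site is told to do and no re-derivation from sums is described.

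**The conflict depends on a reading.** If Best Response means the scan of greatest shrinkage, the main example gives 60 mm under both rules. This stands for any patient whose sum fell below baseline. The documents do not settle which reading applies.

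**Progression need not be late.** A reader might infer that off-treatment PD can only be called too late. That holds for target-lesion sums alone, as the non-target example shows. PD through new lesions needs no sum.

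**The PFS effect is uncertain.** SAP 7.2.4 censors patients who stop for toxicity or other reason at their last adequate assessment, and does not say whether later progression counts. Read literally, some late calls would never enter PFS. Follow-up for progression is also suspended once new cancer treatment starts. This stands for PFS. Duration of response is more exposed, since SAP 7.2.3 censors only when PD is not reached.

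**Arm imbalance is not shown.** A reader might infer a bias toward one arm. AEZS-108 has a proposed maximum of 9 cycles; doxorubicin at 60 mg/m² up to 550 mg/m² allows 550/60 = 9.2, so nine full-dose cycles. Planned duration creates no obvious asymmetry.

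**Later correction.** Section 7.1.5.2 mentions confirmation by a review panel or Principal Investigator, but only for progression in non-target lesions alone.

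**Sections 8.4.5 and 8.5.** Their screening wording can simply identify which lesions are followed, and baseline is the correct reference for PR. They need not be read as setting a PD threshold.

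**Conclusion.** The point holds in limited form and should be corrected. Section 8.6.1 contradicts 7.1.5.1, 7.1.5.3 and 7.1.6 on the reference for progression. When the scan taken as Best Response is not the nadir, following 8.6.1 raises the target-lesion threshold (81.6 mm against 60 mm in the main example) and can delay PD but never advance it. When the two scans coincide there is no effect, and for non-target and new lesions the direction is not fixed.

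The direction for target lesions rests only on the protocol's PD rule. The delays in months rest on invented sums and an assumed doubling time; they show what is possible and are not estimates for this trial. The number of patients affected, the effect on a hazard ratio and any difference between arms cannot be derived from the documents. Duration of response can be lengthened; an effect on PFS is possible but conditional on the SAP censoring row. OS is untouched.

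**What to change.** **Protocol 8.6.1.** Replace the Best Response reference with a sentence such as: *Response is judged against the baseline sum; target-lesion progression is judged against the smallest sum recorded on study (Section 7.1.5.1); non-target and new lesions are judged under Section 7.1.5.2.* A cross-reference to the same rule in 8.4.5 and 8.5 is optional clarification.

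**SAP Appendix B.** State that target-lesion PD will be derived from the recorded sums against the nadir, or that each site call will be checked against that derivation and discrepancies resolved before database lock.

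**Cost.** A wording change and a little programming. Protocol 7.1.3 already requires tumor measurements to be recorded, so no extra scans or data are needed.
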